6.3 Study Termination

The sponsor has the right to terminate study prematurely. Reasons may include efficacy, safety, or futility, among others. Should the sponsor decide to terminate study, the investigator(s) will be notified in writing.

7 STUDY INTERVENTIONS

7.1 Study Drug Administration

Patients will receive HMPL-306 PO QD in a 28-day cycle.

Patients should take HMPL-306 on an empty stomach (no food 2 hours before and 2 hours after dosing) at a relatively fixed time every day with about 240 mL of water. The accurate actual time of dosing should be recorded in patient's pill diary each time.

The best effort should be exerted to ensure patients are medicated according to the study protocol. If the patient misses the study drug for more than 4 hours due to various reasons, it must not be supplemented. The missed dose must be recorded, and the drug will be continued at the next scheduled dosing time. The missed drug must be recorded. If vomiting occurs after drug administration, it should also be recorded, and the drug will be continued at the next scheduled dosing time.

Patients in dose escalation will receive a single dose of HMPL-306 for that cohort dose level, on Day 1 of PK week (7 days prior to C1D1).

7.1.1 Dose Escalation

In dose escalation, dosage will be according to dose level (see [Table 4](#)).

Dose escalation will begin at **[REDACTED]** mg QD of HMPL-306 in a 28-day continuous dosing treatment cycle. The dose will escalate successively according to the sequence of **[REDACTED]** mg QD, **[REDACTED]** mg QD, and **[REDACTED]** mg QD, **[REDACTED]** mg QD, **[REDACTED]** mg QD, **[REDACTED]** mg QD, and **[REDACTED]** mg QD.

PK week: A single oral dose of HMPL-306 will be administered on Day 1 of the PK week (7 days prior to C1D1) for each dose level in dose escalation.

7.1.2 Dose Expansion

In dose expansion, HMPL-306 will be administered PO QD in a 28-day continuous dosing treatment cycle at **[REDACTED]** mg QD dose.

7.2 Description of Products

HMPL-306 will be provided as a tablet formulation of 2 strengths: **[REDACTED]** mg and **[REDACTED]** mg.

7.2.1 Formulation, Storage, Preparation, and Handling

HMPL-306 is formulated as tablets, which are packaged in high-density, polyethylene bottles, with 30 tablets per bottle. The contents of the label will be in accordance with all applicable regulatory requirements.

HMPL-306 should be sealed and stored in a secure, limited-access area under appropriate conditions. Storage temperature should be between **[REDACTED]**°C and **[REDACTED]**°C with **[REDACTED]** **[REDACTED]**. HMPL-306 should not be used beyond the expiration date provided by the sponsor.

Temperature-monitoring log should be recorded and filed in the study binder.

7.2.2 Drug Accountability

7.2.2.1 Assignment/Disposal (Study Site)

All study drug required for this study will be provided by HUTCHMED Limited. The recipient will acknowledge receipt of the study drug by returning the appropriate documentation form indicating shipment content and condition. Damaged supplies will be replaced.

Accurate records of all study drug received at, dispensed from, returned to, and disposed of by the study site should be recorded by using study Drug Inventory Log.

Study drug will be disposed of at the study site according to the study site's institutional standard operating procedure or returned to HUTCHMED Limited or a HUTCHMED Limited-identified entity with appropriate documentation, as determined by the study site. If the study site chooses to destroy/dispose study drug, then the method of destruction/disposal must be documented.

7.2.2.2 Drug Return (Patient)

On Day -2 to Day 1, drug assignment will be performed. The first dose of study drug should be administered on C1D1, except for patients participating in escalation, where they will participate in a mandatory PK week and receive a single dose of HMPL-306 on Day 1 of PK week. Patients will be provided with a pill diary and be instructed on how to account for each day's dose appropriately. Patients should return all unused study drug and containers from the previous cycle on Day 1 (date of scheduled visits) of each subsequent cycle, and new study drug will be dispensed on same day. Site study staff should review patient's pill diary and provide a new diary if necessary on Day 1 visit of each cycle.

If a dose adjustment is required, the patient must return to study site and return all unused study drug. The site must log into the CRF, adjust the dose, reassign the drug serial number, and dispense new study drug dose to the patient. If dose is adjusted a second time, then the site must log into CRF and record the second dose adjustment. On this occasion, it is not necessary to reassign a new drug serial number. If tumor evaluation shows PrD during the previous cycle and the new drug has been dispensed, patient must return all unused study drug on 30-day (± 7 days) safety visit after EOT.

7.3 Assessment and Verification of Compliance

The investigator is responsible for ensuring that patients comply with the treatment schedule. The sponsor will provide supervision through on-site monitoring visits made by its representatives. Investigators should maintain complete and accurate records of drug use. Dosing regimen and patient's actual dosing should be recorded in original treatment records as well as in the CRF. At each treatment visit, the investigator or study staff should comprehensively assess the patient's treatment compliance according to drug dispensing and return status at each visit and actual dosing conditions, such as missed doses and overdosing reported by patient. Study patients must return all drug bottles/containers and remaining capsules at the end of the study. Study sites must return all remaining supplies and drugs to the sponsor or provide evidence of destruction at conclusion of study.

7.4 Prior and Concomitant Therapies

7.4.1 Prohibited Therapies

Any therapy intended for cancer treatment (with exceptions in Section 7.4.2), whether currently marketed or experimental, is prohibited. This includes, but is not limited to, the following: chemotherapy, hormonal therapy, biologic therapy, radiotherapy, or herbal therapy.

Concomitant use of medications that have a known risk of causing QT prolongation (refer to Appendix 6), and/or torsades de pointes is prohibited.

HMPL-306 is a substrate of CCI [REDACTED]. The potential effects of medications that affect PK of HMPL-306 via CCI [REDACTED] pathways have not been tested in humans. Therefore, during treatment period, the use of inducers or inhibitors of CCI [REDACTED] (Appendix 7) should be avoided, and such drugs should be discontinued at least 1 week or 5 half-lives (whichever is longer) before the start of study treatment. Prophylactic use of antiemetic drugs, granulocyte colony stimulating factors (G-CSF), platelet-activating factors, or erythropoietin is not allowed during the DLT assessment window. Outside the DLT assessment window, it may be allowed if the investigator considers it necessary.

7.4.2 Permitted Therapies

Concomitant therapy includes any prescription medications or OTC medications used by a patient. All concomitant medications should be reported to the investigator and recorded on the appropriate CRF.

Patients who use oral contraceptives, hormone-replacement therapy, or other allowed maintenance therapy may continue their use if indicated.

Patients with increased peripheral WBC count (WBC $>25 \times 10^9/L$) and/or who develop differentiation syndrome (DS) during the study treatment period may receive hydroxyurea treatment to reduce peripheral WBCs. In addition, glucocorticoid treatment for DS is also allowed (Section 7.6.1).

Tumor lysis syndrome (TLS) is a potential serious complication of treatment, characterized by large amount of apoptosis or necrosis of tumor cells within a short time by treatment, causing cytological contents to be suddenly released to blood and cause metabolic abnormalities. Preventive medications for this syndrome should also be recorded in concomitant medication form.

Prophylactic use of antiemetic drugs, G-CSF, platelet-activating factors, or erythropoietin is not allowed during the DLT assessment window. Outside the DLT assessment window, it may be allowed if the investigator considers it necessary.

All supportive measures consistent with optimal patient care will be given throughout the study.

7.4.3 Drug-Drug Interactions

There are currently no data on a drug demonstrating clear interactions with HMPL-306 in the human body. In vitro data indicate that HMPL-306 exhibits CCI [REDACTED]
[REDACTED]
[REDACTED]

CCI

During study treatment, the use of medications that are substrates of CCI [REDACTED] (CCI [REDACTED]) should be avoided. If the investigator believes it is necessary to use these medications, consent of the sponsor should be obtained before use, and close observation should be performed during use for probable reduction in efficacy or possible increase in likelihood of toxicity due to drug interactions.

In vitro data show that HMPL-306 has the potential [REDACTED]. Close and frequent monitoring of adverse reactions is recommended with concomitant use of any medication that is a CCI [REDACTED] and has a narrow therapeutic index.

7.4.4 Rescue Therapies

Not applicable.

7.5 Dose Adjustments

7.5.1 Adjustment of Dose Within the DLT Assessment Window

In the DLT assessment window, patients without DLT must not undergo dose reduction of HMPL-306.

- If a DLT occurs, HMPL-306 administration will be suspended and appropriate supportive treatment will be given.
- If a DLT returns to Grade 1 (inclusive) or lower within 14 days, HMPL-306 may be resumed at the previous lower dose if the investigator assesses that the patient may still benefit.
- If a DLT has not returned to Grade 1 (inclusive) or lower within 14 days, or DLT reoccurs at the lowered dose, HMPL-306 treatment will be terminated.
- If a patient experiences a Grade 4 nonhematologic toxicity, HMPL-306 treatment will be terminated.

7.5.2 Dose Adjustment Outside the DLT Assessment Window (Including Dose Expansion Part)

Dose adjustments are to be made for any AE deemed at least possibly related to HMPL-306.

Dose adjustments are to be made as outlined in [Table 8](#) and [Table 9](#).

Table 8 Dose Adjustment for Hematologic Toxicity

CTCAE v5.0 Grade	Action
Grade 1 or 2	None
Grade 3 or 4 (believed to be related to HMPL-306 and NOT underlying disease)	
Hold drug.If the toxicity improves to Grade ≤ 2 within 7 days, then resume at original dose.If the toxicity recurs at original dose, then resume 1 dose level lower provided the toxicity improves to Grade ≤ 2 within 7 days.If the toxicity recurs in setting of prior dose level reduction, then resume 1 additional dose level lower provided the toxicity improves to Grade ≤ 2 within 7 days.In the event the toxicity does not improve to Grade ≤ 2 within 7 days or toxicity recurs despite 2 dose reductions, HMPL-306 treatment is to be permanently discontinued.

CTCAE=Common Terminology Criteria for Adverse Events.

Table 9 Dose Adjustment for Nonhematologic Toxicity

CTCAE v5.0 Grade	Action
Grade 1 or 2	None
Grade 3	
Hold drug.If the toxicity improves to Grade ≤ 2 within 7 days, then resume at original dose.If the toxicity recurs at original dose, then resume 1 dose level lower provided the toxicity improves to Grade ≤ 2 within 7 days.If the toxicity recurs in setting of prior dose level reduction, then resume 1 additional dose level lower provided the toxicity improves to Grade ≤ 2 within 7 days.In the event the toxicity does not improve to Grade ≤ 2 within 7 days or toxicity recurs despite 2 dose reductions, HMPL-306 treatment is to be permanently discontinued.
Grade 4	Permanently discontinue treatment with HMPL-306.

CTCAE=Common Terminology Criteria for Adverse Events.

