6.2.2 Study Stopping Rules

Safety will be monitored continuously throughout the conduct of the study by a standing SRC. There will be periodic review of emerging data on safety, PK, drug exposure, TE, PD, and clinical response to determine continuation (or otherwise) of individual patient, cohorts, arms, or entire dose expansion part. If the study is halted as per Study Stopping Rules (Section 6.2.2.2) in either the dose escalation part or the dose expansion part, the study will only be restarted after Regulatory Approval as per local regulations.

Dose stopping rules for individual patients common to both dose escalation and dose expansion parts include:

1. DLTs that occur outside the DLT assessment window (DLT-equivalent) that have not resolved to Grade 1 or lower within 14 days, or after medical intervention as specified in Section 4.1.1.
2. Progression of disease that leads to treatment discontinuation
3. In the opinion and recommendation of the PI, or individual patient on their own, may withdraw from study at any time
4. If there is documented evidence of repeated non-compliance

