6.2.2.1 Stopping Rules for Individual Patient

Dose Escalation:

Dosing will stop for an individual patient if:

DLT has not returned to Grade 1 or lower within 14 days

See Section 4.1.1 for details on dose escalation Part 1, DLT, and safety assessment.

Dose Expansion:

1. DLT-equivalent event has not resolved (even with medical intervention) within 14 days, or has re-occurred again at a de-escalated dose level
2. Resolution in severity (down-grade) and/or duration (within 14 days) of DLT-equivalent event will determine dose interruption, reduction, or discontinuation for the individual
3. Resolution of DLT-equivalent event will determine if the patient will resume treatment, at the discretion of investigator, at:
 - the same dose level
 - a lower dose
 - discontinue treatment altogether

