7.5.4 General Dose Adjustment Note

The severity of DLTs/AEs will be graded according to the NCI CTCAE v5.0. Reasons for dose modifications or delays, the supportive measures taken, and outcome should be documented in patient's chart and recorded in the CRF.

- For any concomitant conditions already apparent at baseline, dose modifications will apply according to corresponding shift in toxicity grade, if investigator feels it is appropriate. For example, if a patient has Grade 1 asthenia at baseline that increases to Grade 2 during treatment, this will be considered a shift of 1 grade and treated as Grade 1 toxicity for dose-modification purposes.
- For toxicities that are considered by investigators to be unlikely to develop into serious or life-threatening events, treatment can be continued at the same dose.
- To recover from acute toxicity, unless otherwise indicated, treatment can be delayed for up to 14 days. If a treatment delay is required for 14 days or longer, treatment should be discontinued. Continuation/resumption of treatment after an interruption of 14 days or more must be discussed with the sponsor.
- Where several toxicities with different grades or severity occur at the same time, dose modifications should be according to highest grade observed.

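### For drug-related DLT-equivalent events outside the DLT window, Tables 8–9 and Sections 6.2.2 and 6.2.2.1 give inconsistent individual stopping rules, with no precedence stated

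*Protocol*

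**What the plan says.** Protocol Section 7.5.2 is headed "Dose Adjustment Outside the DLT Assessment Window (Including Dose Expansion Part)". For toxicity at least possibly related to HMPL-306, Tables 8 and 9 hold the drug and resume it at the original dose if the event falls to Grade 2 or lower within 7 days. On recurrence they go down one dose level. On recurrence after that reduction the instruction is "then resume 1 additional dose level lower provided the toxicity improves to Grade" 2 or lower within 7 days. If the 7-day limit is missed or "toxicity recurs despite 2 dose reductions, HMPL-306 treatment is to be permanently discontinued". Section 6.2.1.1 makes discontinuation for intolerable toxicity mandatory and points to Tables 8 to 10 for it.

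Section 6.2.2 lists individual stopping rules common to both parts. The first covers "DLTs that occur outside the DLT assessment window (DLT-equivalent) that have not resolved to Grade 1 or lower within 14 days".

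Section 6.2.2.1, under dose expansion, stops a patient when a "DLT-equivalent event has not resolved (even with medical intervention) within 14 days, or has re-occurred again at a de-escalated dose level". For events that do resolve, it leaves the choice between the same dose, a lower dose and stopping to the investigator.

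**The concern.** Tables 8–9 and Section 6.2.2 both act on the same event in the same period, but with different recovery grades and time limits. Section 6.2.2.1 adds a recurrence rule for expansion that differs from the tables. A site reading Section 7.5.2 alone could resume a patient whom a site reading Section 6.2.2 would stop.

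The first stake is patient safety, because these are stopping rules. The second is interpretation. Safety and tolerability are the primary objective, and discontinuations, dose reductions and relative dose intensity are planned summaries (protocol Section 9.2.4; SAP Sections 5.2.10 and 5.2.11.2). For the affected events, those entries may reflect which section was followed as well as how the drug was tolerated.

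**Working it through.** No sample-size or power figure is involved, so the check compares the rules by scope and then by outcome.

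**Step 1: the rules side by side, outside the DLT window.**

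| | Tables 8–9 (7.5.2) | 6.2.2 | 6.2.2.1, expansion |
|---|---|---|---|
| Events | Related Grade 3 or 4 hematologic; related Grade 3 nonhematologic (Grade 4 nonhematologic stops outright) | DLT-equivalent | DLT-equivalent |
| Recovery needed | Grade 2 or lower | Grade 1 or lower | Resolved, no grade given |
| Time limit | 7 days | 14 days | 14 days |
| Recurrence after one reduction | Second reduction | No rule | Stop |
| Part | Both | Both | Expansion only |

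**Step 2: the overlap.** It is the set of drug-related events that would be DLTs under Section 8.1.3 had they occurred in the window. A related Grade 3 nonhematologic event lasting more than 72 hours qualifies. Section 8.1.3 leaves out shorter nonhematologic Grade 3 events, neutropenia of 7 days or less, Grade 3 thrombocytopenia without bleeding or platelet transfusion, and neutropenia or thrombocytopenia with active leukemia. For those, Tables 8–9 have no competitor.

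**Step 3: time and grade.** Let d2 be the day the event first reaches Grade 2 or lower and d1 the day it reaches Grade 1 or lower, with d2 ≤ d1. The tables stop permanently if d2 > 7. Section 6.2.2 stops if d1 > 14. There are four outcomes:

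- d2 ≤ 7 and d1 ≤ 14: neither stops.
- d2 ≤ 7 and d1 > 14: the tables resume, 6.2.2 stops. Example: Grade 2 on Day 5, still Grade 2 after Day 14.
- d2 from 8 to 14 and d1 ≤ 14: the tables stop permanently, 6.2.2 has no stop trigger. Example: Grade 2 on Day 10, Grade 1 by Day 14.
- d2 > 7 and d1 > 14: both stop.

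As an illustration, count the pairs with 1 ≤ d2 ≤ d1 ≤ 21, which is 21 × 22 / 2 = 231. Neither rule stops in 14 + 13 + … + 8 = 77. The tables resume and 6.2.2 stops in 7 × 7 = 49. The tables stop and 6.2.2 is silent in 7 + 6 + … + 1 = 28. Both stop in 49 + 28 = 77. The 21-day horizon is an assumption. With a horizon of L days (L at least 14) the two disagreement counts are 7 × (L − 14) and 28. These are counts of patterns, not probabilities. They show only that the difference runs in both directions.

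**Step 4: recurrence, expansion only.** Under the tables: first event, original dose; first recurrence, one level lower; recurrence at that level, one further level lower; recurrence after two reductions, stop. Section 6.2.2.1 stops at the third of these steps. A first recurrence at the original dose is a stop under neither.

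**Step 5: precedence.** Section 6.2.1.1 makes the tables binding but does not say they displace 6.2.2. Sections 6.2.2 and 6.2.2.1 do not mention the tables.

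**The case against.** The strongest reply is that the sections can be followed together. Section 6.2.2 lists reasons to stop; it does not order a site to continue when no reason is met. A site that stops whenever either trigger is met satisfies both time limits. In the resume-then-stop pattern it can restart by Day 7 and stop after Day 14 if the event is still above Grade 1. This stands in part: a reader might infer that no site can comply with both limits, and the documents do not support that. But the either-trigger reading is written nowhere. For an event that has settled at Grade 2, Tables 8–9 prescribe no action, so a site using the tables alone has no reason to stop. Nor does this reading make the two recurrence instructions agree. It would leave the tables' second-reduction step unused for DLT-equivalent events in expansion.

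Other stronger readings also fail:

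- That the conflict covers every related Grade 3 event. It covers only DLT-equivalent ones.
- That 6.2.2.1 stops at the first recurrence. It stops at recurrence on a reduced dose.
- That 6.2.2 and 6.2.2.1 form a single rule. The former has the Grade 1 threshold and no recurrence rule; the expansion rule has recurrence and no grade.
- That 7.5.1 and 7.5.4 conflict as well. Section 7.5.1 applies inside the window. Section 7.5.4 says "treatment can be delayed for up to 14 days" only where nothing else is specified, so it can defer to the tables.

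On scale, the footnote to SAP Table 13 reports one patient in expansion Cohort A, pooled with escalation Cohort 8. That limits the recurrence clash to at most that patient.

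**Conclusion.** The inconsistency is real but narrow. For drug-related DLT-equivalent events outside the DLT window, the tables and Section 6.2.2 differ on recovery grade and time limit in both parts of the study. The tables and Section 6.2.2.1 give opposite instructions on recurrence after one reduction in expansion. No precedence is stated.

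The grade and time difference can reach any escalation patient with such an event after the window; the documents do not say how many there were. A reader might conclude that the discontinuation, reduction and dose-intensity results as a whole depend on which section a site used. The documents do not support that; the effect is confined to these events.

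The conclusion assumes that DLT-equivalent means an event meeting the Section 8.1.3 criteria outside the window, as Section 6.2.2 implies. SAP Section 7 drops the DLT-equivalent analysis because investigators' assessments against the DLT criteria were poorly documented in the data capture system. It may therefore be hard to reconstruct afterwards which rule applied. Clarification is worth making because it is cheap and concerns patient safety and the primary objective.

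**What to change.** The sponsor should reconcile Sections 6.2.2, 6.2.2.1 and 7.5.2 (Tables 8–9) on recovery grade, time limit and recurrence, or state which section governs DLT-equivalent events outside the DLT window. That is a protocol clarification and needs no new data collection. If dosing has ended, the study report should state which rule was applied to each toxicity-related stop or reduction. This costs a case-by-case review, possibly with site queries given the documentation gap. Which rule is clinically right is for the sponsor and investigators to decide; this review proposes none.

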7.5.3 Dose Adjustment for QT Interval Prolongation

Table 10 Dose Adjustment for QT Interval Prolongation

Degree of QTcF Prolongation	Action
QTcF greater than 480 ms to 500 ms	
Hold drug.Monitor and supplement electrolyte levels as clinically indicated.Review and adjust concomitant medications with known QTcF interval-prolonging effects.Restart HMPL-306 at original dose if QTcF interval returns to less than or equal to 480 ms.Monitor ECGs at least weekly for 2 weeks following resolution of QTcF prolongation.
QTcF greater than 500 ms and/or QTcF interval prolongation with signs/symptoms of life-threatening arrhythmia	
Discontinue HMPL-306 permanently.Initiate continuous ECG monitoring and immediate clinical evaluation.

ECG=electrocardiogram; QT=interval from the start of the Q wave to the end of the T wave; QTcF=QT interval corrected for heart rate using Fridericia's formula.

